4.2.3.1. Participant Input into Design

Twelve patients and caregivers were interviewed in order to better understand what symptoms are most burdensome to patients and what might impact their decision to participate in a clinical study. All patients had cancer (prostate, non-small cell lung, colorectal or pancreatic cancers) and had experienced significant unintentional weight loss and other symptoms of cachexia.

Patient input was valuable in informing key outcomes. Of greatest interest were improved appetite and reduced fatigue, supporting the choice of appetite as the primary endpoint for the study.

Patients and caregivers also provided input on the study design which triggered incorporation of options to potentially enhance patient participation and retention, and highlighted the following additional considerations which are anticipated to be of value to patients:

[figure not shown]
[figure not shown]
- Option for home/tele-visits with physician or in-person physician appointments where feasible through double-blind portion of the study.
- Nutritional consultations eg, via TeleHealth. This will be included, if operationally feasible.
- Confirmed the importance to patients of including the option to receive open-label treatment following double-blind period.

- Patients emphasized the significance of having their overall experiences with the study treatment heard by the Sponsor. This led to the incorporation of qualitative phone interviews in order to facilitate a more holistic assessment.
- Highlighted the value of appropriate training, including to home HCPs, on important aspects of the disease and the potential social and psychological impact.

CCI

CCI

CCI

CCI

CCI

CCI

CCI

4.4. End of Study Definition

A participant is considered to have completed the study if he/she has either completed Part A (including follow-up), or has completed Part A and has entered, and completed, the OL extension Part B.

The end of the study is defined as the date of the last visit of the last participant in the study.

5. STUDY POPULATION

This study can fulfill its objectives only if appropriate participants are enrolled. The following eligibility criteria are designed to select participants for whom participation in the study is considered appropriate. All relevant medical and nonmedical conditions should be taken into consideration when deciding whether a particular participant is suitable for this protocol.

Prospective approval of protocol deviations to recruitment and enrollment criteria, also known as protocol waivers or exemptions, is not permitted.

5.1. Inclusion Criteria

Participants are eligible to be included in the study only if all the following criteria apply:

Age and Sex:

1. Male or female participants ≥ 18 (or the minimum country-specific age of consent if >18) at Screening.
 - Refer to [Appendix 4](#) for reproductive criteria for male ([Section 10.4.1](#)) and female ([Section 10.4.2](#)) participants.

Type of Participant and Disease Characteristics:

2. Documented diagnosis of non-small cell lung, pancreatic, colorectal, prostate, breast or ovarian cancer which, in the treating oncologist's assessment, is considered advanced, for example:
 - Unresectable Stage III or IV **non-small cell lung** cancer.
 - Locally advanced or metastatic **pancreatic adenocarcinoma**.
 - Metastatic or recurrent **colorectal** cancer.
 - Metastatic **prostate** cancer.
 - Metastatic or recurrent **breast** cancer.
 - Refractory **ovarian** cancer.
3. Meets any of the following criteria at Randomization:
 - i. Not currently receiving antineoplastic therapy. This may be, for example, a patient who:
 - Has chosen not to receive further therapy, for example for quality of life reasons;
 - Is not indicated for future antineoplastic therapy or has exhausted all treatment options;
 - Has stable disease where no antineoplastic therapy is judged to be necessary;
 - Is taking a break between antineoplastic treatments, where the break has begun at least 4 weeks prior to Randomization and is anticipated to be longer than the 6-week duration of the double-blind portion of this study.If such a patient has recently completed a course of antineoplastic therapy, the last dose of that therapy should be at least 4 weeks prior to Randomization (see [Section 6.5](#)).
 - ii. Patients on standard of care systemic antineoplastic therapy or treatment without curative intent, (see [Section 6.5](#)).
4. Anorexia as defined by a score **CCI** in the Cancer-Related Cachexia Symptom Assessment-Appetite 7-day recall scale (see [Appendix 7](#)) at Screening and Randomization.

5. Serum GDF-15 levels of **CCI** (as measured using the Investigational Use Only Roche Elecsys GDF 15 assay)³⁰ at Screening.
6. Participants who are assessed by the investigator to be **able to participate** for the double-blind treatment period of **6 weeks**. In the investigator's judgement, the participant should be anticipated to be able to comply with all scheduled visits, treatment plan, laboratory tests, lifestyle considerations, and other study procedures during the double-blind portion of the study.

In cases where the investigator is not the treating oncologist, the oncologist's assessment of the potential participant's suitability for inclusion must also be considered.

Informed Consent:

7. Capable of giving signed informed consent as described in [Appendix 1](#), which includes compliance with the requirements and restrictions listed in the ICD and in this protocol.
8. Willing to comply with all scheduled visits, treatment plan, laboratory tests, contraception guidelines, and other study procedures for at least the 6-week double-blind treatment period.

5.2. Exclusion Criteria

Participants are excluded from the study if any of the following criteria apply:

Medical Conditions:

1. Receiving tube feedings or parenteral nutrition (either total or partial) at the time of Screening or Randomization.
2. Current active reversible causes of decreased food intake, as determined by the Investigator. These causes may include, but are not limited to:
 - Mechanical obstructions making patient unable to eat;
 - National Cancer Institute (NCI) Common Terminology Criteria for Adverse Events (CTCAE) Grade 3 or 4 oral mucositis.
3. Unresolved acute effects of any prior therapy, or uncontrolled symptoms (eg, pain, diarrhea) at Randomization that in the judgement of the PI makes the participant unsuitable for the study. For example, uncontrolled pain may be indicated by a recent (eg, within past 15 days) change in opioid treatment.
4. Current, severe gastrointestinal disease (including esophagitis, gastritis, malabsorption) at Randomization.

5. History of gastrectomy.
6. Persistent symptoms due to ascites at randomization, unresponsive to clinically indicated interventions.
7. Participants with known symptomatic brain metastases requiring steroids.
Participants with asymptomatic or previously diagnosed brain metastases are eligible if they have completed their treatment and have recovered from the acute effects of radiation therapy or surgery prior to Screening, have discontinued corticosteroid treatment for these metastases and are neurologically stable for at least 4 weeks (requires magnetic resonance imaging [MRI] confirmation) prior to Screening.
Note that if radiation therapy becomes necessary for treatment of brain metastases or palliative treatment after Randomization, this will not be a reason for discontinuation.
8. Participants with active, uncontrolled bacterial, fungal, or viral infection, including but not limited to HBV, HCV, HIV or participants with known AIDS-related illness.
9. Undergoing major surgery (central venous access placement and tumor biopsies are not considered major surgery) within **4 weeks** prior to first dose of investigational product. Patient must be well recovered from acute effects of surgery prior to screening. Patient should not have plans to undergo major surgical procedures during the study.
10. Other medical or psychiatric condition including recent (within the past year) or active suicidal ideation/behavior or laboratory abnormality that may increase the risk of study participation or, in the investigator's judgment, make the participant inappropriate for the study.

Prior/Concomitant Therapy:

Part A Double-Blind treatment period only:

11. Initiation of new systemic antineoplastic therapy (eg, chemotherapy, immunotherapy) within the **4 weeks** prior to the first dose of investigational product or planning to initiate antineoplastic therapy during the 6-week double-blind portion of the study.
12. Initiation of new treatment prescribed or self-administered and known to have an impact on anorexia, weight loss or cachexia, including but not limited to mirtazapine, olanzapine, cannabinoids, within the **4 weeks** prior to the first dose of investigational product or during the 6-week double-blind portion of the study; stable (ie, no significant change to dosage or frequency of administration in prior 4 weeks) therapy is permissible. See [Section 6.5](#) Concomitant Therapy for details.

13. Radiation therapy other than localized palliative treatment (eg, pain management for bone metastases) within the **3 weeks** prior to the first dose of investigational product or during the 6-week double-blind portion of the study.
14. Initiation of new treatment with systemic glucocorticoids within the **4 weeks** prior to the first dose of investigational product or during the 6-week double-blind portion of the study; stable (ie, no significant change to dosage or frequency of administration in prior 4 weeks) steroid therapy eg, dexamethasone as part of pre-medication or daily oral prednisone is permissible. See [Section 6.5](#) Concomitant Therapy for details.
15. Initiation of megestrol acetate within the **2 weeks** prior to the first dose of investigational product or during the 6-week double-blind portion of the study; stable (ie, no significant change to dosage or frequency of administration in prior 2 weeks) therapy is permissible. See [Section 6.5](#) Concomitant Therapy for details.

Part B Open-Label treatment period: there are no restrictions on initiation of new therapy or changes to existing therapy during open-label treatment.

Prior/Concurrent Clinical Study Experience:

16. Received previous treatment with at least one dose of PF-06946860.
17. Actively receiving a concurrent investigational agent, or previous administration with an investigational drug within 30 days (or as determined by the local requirement) or 5 half-lives preceding the first dose of investigational product used in this study (whichever is longer).

Diagnostic Assessments:

18. Positive urine drug screen for illicit drugs at Screening, with the exception of cannabinoids per Prior/Concomitant Therapy criteria number [12](#) above. Results may be confirmed by a single repeat, if necessary. In addition, drugs which have been medically prescribed and reported to the investigator at the Screening visit may be permitted, if judged appropriate by the investigator and permitted by the Sponsor. Prescribed pain medications (eg, opioids, morphine, hydrocodone) do not need be cleared with the Sponsor.
19. Inadequate liver function at Screening as evidenced by any 1 of the following, which may be confirmed by a single repeat, if necessary:
 - Total serum bilirubin $>1.5 \times$ upper limit of normal (ULN) unless the participant has documented Gilbert syndrome;
 - Aspartate (AST) and/or Alanine aminotransferase (ALT) $>3 \times$ ULN; $>5.0 \times$ ULN if there is liver involvement by the tumor;

- Alkaline phosphatase $>3 \times$ ULN. Inclusion of participants with alkaline phosphatase $>3 \times$ ULN may be acceptable if they are deemed medically stable and fit for the study by both investigator and sponsor medically qualified personnel.

20. Inadequate renal function at Screening, including creatinine >2 mg/dL, or calculated Glomerular Filtration Rate (GFR) <30 mL/minute/1.73 m² as calculated by the modification of diet in renal disease (MDRD) equation.³¹ Result may be confirmed by a single repeat, if necessary.

Other Exclusions:

21. Woman who is pregnant or breast-feeding.
22. Investigator site staff or Pfizer employees directly involved in the conduct of the study, site staff otherwise supervised by the investigator, and their respective family members.

5.3. Lifestyle Considerations

5.3.1. Contraception

The investigator or his or her designee, in consultation with the participant, will confirm that the participant has selected an appropriate method of contraception for the individual participant and his or her partner(s) from the permitted list of contraception methods (see [Appendix 4 Section 10.4.4](#)) and will confirm that the participant has been instructed in its consistent and correct use. At time points indicated in the [SoA](#), the investigator or designee will inform the participant of the need to use highly effective contraception consistently and correctly and document the conversation and the participant's affirmation in the participant's chart (participants need to affirm their consistent and correct use of at least 1 of the selected methods of contraception). In addition, the investigator or designee will instruct the participant to call immediately if the selected contraception method is discontinued or if pregnancy is known or suspected in the participant or partner.

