10.4.2. Female Participant Reproductive Inclusion Criteria

A female participant is eligible to participate if she is not pregnant or breastfeeding, and at least 1 of the following conditions applies:

- Is not a WOCBP (see definitions below in [Section 10.4.3](#)).

OR

- Is a WOCBP and using a contraceptive method that is highly effective (with a failure rate of <1% per year), preferably with a low user dependency, as described below, during the intervention period and for at least 22 weeks after the last dose of study intervention, which corresponds to the time needed to eliminate any reproductive safety risk of the study intervention(s). If a highly effective method that is user dependent is chosen, a second effective method of contraception, as described below, must also be used. The investigator should evaluate the effectiveness of the contraceptive method in relationship to the first dose of study intervention.

- Is a WOCBP and using a contraceptive method that is highly effective (with a failure rate of <1% per year), with high user dependency, as described below during the intervention period and for at least 22 weeks after the last dose of study intervention, which corresponds to the time needed to eliminate any reproductive safety risk of the study intervention(s). In addition, a second effective method of contraception, as described below, must be used. The investigator should evaluate the effectiveness of the contraceptive method in relationship to the first dose of study intervention.

The investigator is responsible for review of medical history, menstrual history, and recent sexual activity to decrease the risk for inclusion of a woman with an early undetected pregnancy.

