10.11. Appendix 11 Study Conduct

10.11.1. Telehealth Visits

Telehealth visits may be conducted during this study and used to assess participant safety and collect data points. Telehealth includes the exchange of healthcare information and services via telecommunication technologies (eg, audio, video, video-conferencing software) remotely, allowing the participant and the investigator to communicate on aspects of clinical care, including medical advice, reminders, education, and safety monitoring. Assessments to be performed during a telehealth visit are outlined in the [SoA](#), and may include:

- Review and record study intervention(s), including compliance and missed doses.
- Review and record any AEs and SAEs since the last contact. Refer to [Section 8.3](#).
- Review and record any new concomitant medications or changes in concomitant medications since the last contact.
- Review and record contraceptive method and results of pregnancy testing. Confirm that the participant is adhering to the contraception method(s) required in the protocol. Refer to [Appendix 4](#).

Study participants must be reminded to promptly notify site staff about any change in their health status.

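### Protocol 5.3.1 asks participants to affirm only one contraceptive method, although 10.4.2 requires two when a woman's highly effective method is user dependent

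*Protocol*

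**What the plan says.** **The recurring check (Protocol 5.3.1).** At the times in the Schedule of Activities, the investigator or designee must "inform the participant of the need to use highly effective contraception consistently and correctly", and must document the conversation and the participant's affirmation. The content of that affirmation is given in a parenthesis: "participants need to affirm their consistent and correct use of at least 1 of the selected methods of contraception". Staff must also "instruct the participant to call immediately if the selected contraception method is discontinued". Methods are to be selected from the permitted list in 10.4.4. The section does not refer to 10.4.2.

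**The rule on use (Protocol 10.4.2).** The rule appears in two bullets. The first, on methods preferably of low user dependency, adds: "If a highly effective method that is user dependent is chosen, a second effective method of contraception, as described below, must also be used". The second, on methods of high user dependency, says: "In addition, a second effective method of contraception, as described below, must be used". Both apply "during the intervention period and for at least 22 weeks after the last dose of study intervention".

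**The telehealth check (Protocol 10.11.1).** Among the assessments that a telehealth visit may include is: "Confirm that the participant is adhering to the contraception method(s) required in the protocol". This wording follows whatever number of methods the protocol requires of the participant.

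**The concern.** Protocol 4.2.1 requires highly effective contraception because the drug's developmental toxicity has not been studied. Appendix 4 turns this into rules that differ by type of participant, with a back-up method added where the main one depends on the user. The review in 5.3.1 is how the site records, over the course of the study, that those rules are being kept.

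A record of compliance should ask about the thing to be complied with. For one group, 5.3.1 asks about less than 10.4.2 demands, so a correctly completed chart entry can coexist with a breach. A monitor who reads the chart would have no prompt to look further. What is at stake is the loss of an intended back-up going unnoticed; no efficacy or safety analysis depends on it.

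**Working it through.** There is no figure to reproduce. The check sets the number of methods required beside the number affirmed, for each type of participant.

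| Participant | Use required (Appendix 4) | Affirmation required (5.3.1) | Mismatch |
|---|---|---|---|
| Man (10.4.1) | Abstinence or a condom, plus no sperm donation: 1 method | At least 1 | No |
| Woman of childbearing potential, low-user-dependency method (10.4.2) | 1 method | At least 1 | No |
| Woman of childbearing potential, user-dependent method (10.4.2) | 2 methods | At least 1 | Yes |

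The mismatch is confined to the third row. The protocol clearly expects that such women may enrol:
- Adults from 18 years are eligible, and breast and ovarian cancer are among the tumour types (5.1).
- Hormonal contraceptives that meet the study's requirements are allowed in women of childbearing potential (6.5).
- Combined hormonal methods, and oral or injectable progestogen-only methods, are listed as user dependent (10.4.4).

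Next, does the meaning of a selected method rescue the wording? There are two possible readings:
1. The second effective method counts as a selected method. The woman has then selected two, and affirming one of them is enough for 5.3.1.
2. It does not count, because 5.3.1 takes its methods from 10.4.4 and the text supplied there lists only highly effective ones. The affirmation then does not reach the second method at all.

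Under either reading, a woman who keeps her user-dependent highly effective method and stops the second can affirm truthfully. The gap therefore does not depend on which reading is right.

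The discontinuation instruction has the same weakness. It speaks of one selected method in the singular, so it does not clearly tell a woman who must use two to call when she stops the second.

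**The case against.** The strongest reply is that the affirmation is a common minimum, in a section written for both sexes, and that the actual rule is secured elsewhere. Much of this is right:
- Section 10.4.2 remains binding. Inclusion criterion 1 points to it, and eligibility is reviewed at both Screening and Randomization.
- Inclusion criterion 7 commits participants to the requirements of the consent document and protocol, without limiting this to Part A. A reader might infer from criterion 8, which speaks of "contraception guidelines, and other study procedures for at least the 6-week double-blind treatment period", that the contraception commitment lapses in Part B. Criterion 7 and the duration stated in 10.4.2 rule that out.
- Telehealth visits may include a check in the right terms. It is optional in its wording, however, and the telehealth visit is not held when the participant attends the clinic.
- Section 8.2.3 requires pregnancy tests at scheduled times, after a missed cycle and at the end of the study. These detect a failure; they do not prevent one.

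These controls limit the consequence and justify a low grade. None changes what the chart is asked to record during treatment. The common-minimum argument explains how the wording arose but does not require it, since a standard of every method required of that participant suits all three rows of the table.

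A reader might go further and infer that a woman could drop her highly effective method, keep only a merely effective one, and still be charted as compliant, falling below the 4.2.1 requirement. The documents do not support this. Section 5.3.1 draws selected methods from 10.4.4, whose supplied text lists only highly effective methods, and the same sentence ties the affirmation to being told of the need for highly effective contraception. A woman relying on the back-up alone could not properly give it.

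**Conclusion.** The inconsistency is real and minor. For women of childbearing potential on a user-dependent method, the affirmation in 5.3.1 is one method short of 10.4.2, so the loss of the required second method can pass the recurring check. A woman in that position is still on a highly effective method; what she has lost is the back-up. It would be wrong to conclude that 5.3.1 relaxes the two-method rule: it sets only what the chart must show.

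The number of women concerned is not given. With about 40 participants randomised and only part of them women of childbearing potential, it is probably small and may be zero. No estimand, analysis, sample size or dosing decision changes. The conclusion rests on the literal wording of 5.3.1 and 10.4.2, and assumes that site documents not supplied, such as chart templates, do not already ask about both methods.

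**What to change.** Make two changes in Protocol 5.3.1:
1. Replace the one-method minimum with affirmation of all contraception methods that Appendix 4 requires for that participant, stating that this means two when the highly effective method is user dependent. The wording of 10.11.1 about the methods required in the protocol can serve as the model.
2. Apply the instruction to call on discontinuation to any required method.

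A clarification letter or the next amendment would do. The cost is two phrases, with no new visit, test or procedure. While editing, confirm that 10.4.4 describes the second effective methods to which 10.4.2 refers. None is visible in the text supplied, which may only reflect how the PDF was read.
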